## **h. Study Procedure**

- *Treatment Arms*
- *Arm 1: Intervention*
- *Arm 2: Placebo*
- *Intervention Description, Dosage and Route of Administration*
- *The investigational product is rituximab, which is a monoclonal antibody against CD20 that cause lysis of B-lymphocytes. The antibody is a humanised mouse antibody and is administered intravenously via an infusion over a period of time that varies according to the dosage (see below). The dosage to be used is 100 mg/m^2 of estimated body surface area (BSA). BSA will be estimated based on height (H) and weight (W) according to the Du Bois formula:*
- *BSA = 0.007184 x W0.425 x H0.725*
- *With height measured in cm and weight measured in kg.*
- *Dosage will be rounded down to the nearest 10 mg.*
- *Study drug will be provided as a solution of 100 mg in 10 ml vials.*
- *Infusions will be delivered at set times of 10 weeks and 30 weeks after administration of alemtuzumab in combination with 100 mg intravenous methylprednisolone to reduce the risk of infusion reactions.*
- *Placebo*

- *Placebo will be 0.9% sodium chloride, which as a colourless solution is indistinguishable from diluted rituximab.*
- *Pre-medication*
- *Prior to administration of the study drug/placebo all trial participants (intervention and placebo arms) will be administered loratadine 10 mg orally and 100 mg intravenous methylprednisolone made up in 100 ml 0.9% sodium chloride and infused over 30 minutes.*
- *Preparation and Administration of Study Drug/Placebo*
- *Study drug and placebo will be made up by non-blinded onsite pharmacists according to the randomisation schedule product information sheet for rituximab. Specifically, the calculated dose of study drug will be aseptically withdrawn from vials and diluted in 100 ml of 0.9% sodium chloride ensuring that the calculated concentration is between 1 mg/ml and 4 mg/ml. To ensure adequate mixing the bag of diluted study drug/placebo will be gently inverted to avoid foaming. The prepared drug products will be visually inspected for particulate matter or discolouration.*
- *Rituximab/placebo will be administered according to Tables 1 and 2 below:*

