**Table 1: First Dose administration rate of Rituximab/Placebo**

Period	1-30 mins			31-60 mins			61-90 mins			91-120 mins			Total		
Infusion Rate	50 mg/hr			100 mg/hr			150 mg/hr			200 mg/hr					
BSA (m  )	Time (m)	Dose (mg)	Vol (ml)	Time (m)	Dose (mg)	Vol (ml)	Time (m)	Dose (mg)	Vol (ml)	Time (m)	Dose (mg)	Vol (ml)	Time (m)	Dose (mg)	Vol (ml)
1.5	30	25	16.7	30	50	33.3	30	75	50.0	0	0	0.0	90	150	100.0
1.6	30	25	15.6	30	50	31.3	30	75	46.9	3	10	6.3	93	160	100.0
1.7	30	25	14.7	30	50	29.4	30	75	44.1	6	20	11.8	96	170	100.0
1.8	30	25	13.9	30	50	27.8	30	75	41.7	9	30	16.7	99	180	100.0
1.9	30	25	13.2	30	50	26.3	30	75	39.5	12	40	21.1	102	190	100.0
2	30	25	12.5	30	50	25.0	30	75	37.5	15	50	25.0	105	200	100.0
2.1	30	25	11.9	30	50	23.8	30	75	35.7	18	60	28.6	108	210	100.0
2.2	30	25	11.4	30	50	22.7	30	75	34.1	21	70	31.8	111	220	100.0
2.3	30	25	10.9	30	50	21.7	30	75	32.6	24	80	34.8	114	230	100.0
2.4	30	25	10.4	30	50	20.8	30	75	31.3	27	90	37.5	117	240	100.0
2.5	30	25	10.0	30	50	20.0	30	75	30.0	30	100	40.0	120	250	100.0

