**Table 2: Subsequent dose administration rate of Rituximab/Placebo**

Period	1-30 mins			31-60 mins			61-90 mins			Total		
Infusion Rate	100 mg/hr			200 mg/hr			300 mg/hr					
BSA (m  )	Time (m)	Dose (mg)	Vol (ml)	Time (m)	Dose (mg)	Vol (ml)	Time (m)	Dose (mg)	Vol (ml)	Time (m)	Dose (mg)	Vol (ml)
1.5	30	50	33.3	30	100	66.7	0	0	0.0	60	150	100.0
1.6	30	50	31.3	30	100	62.5	2	10	6.3	62	160	100.0
1.7	30	50	29.4	30	100	58.8	4	20	11.8	64	170	100.0
1.8	30	50	27.8	30	100	55.6	6	30	16.7	66	180	100.0
1.9	30	50	26.3	30	100	52.6	8	40	21.1	68	190	100.0
2	30	50	25.0	30	100	50.0	10	50	25.0	70	200	100.0
2.1	30	50	23.8	30	100	47.6	12	60	28.6	72	210	100.0
2.2	30	50	22.7	30	100	45.5	14	70	31.8	74	220	100.0
2.3	30	50	21.7	30	100	43.5	16	80	34.8	76	230	100.0
2.4	30	50	20.8	30	100	41.7	18	90	37.5	78	240	100.0
2.5	30	50	20.0	30	100	40.0	20	100	40.0	80	250	100.0

- 
- *First infusions will typically run over 90 – 120 minutes and subsequent infusions will run over 60 – 80 minutes.*
  - *Pulse and blood pressure will be monitored every 30 minutes from the commencement methylprednisolone and until 30 minutes after the completion of rituximab/placebo and for no less than a minimum of 2 hours.*
  - *Infusion rates should only be increased to the next phase provided there are no adverse events and that if there are symptoms of a mild infusion reaction the rate should be reduced to the previously tolerated level or if symptoms are more significant (shortness of breath, tachycardia, low blood pressure) the infusion should be discontinued and the PI notified immediately.*
  
  - *Study Drug Accountability*
  - *A nominated pharmacist at each participating site will maintain an inventory of receipt, use, return and collection of study drug.*
  - *Control of Supplies*
  - *The nominated site pharmacist at each site is responsible for recording the dispensing of the product to participants on an investigational product dispensing log which will be recorded in the eCRF. Accurate records will be maintained demonstrating dates and amount of product received, to whom dispensed and accounts of any product accidentally or deliberately destroyed. Clinical trial materials will not be loaned or dispensed to another investigator or trial centre or used for any purpose other than the trial without the prior approval of the trial coordinator and Site Investigator.*
  - *Return of Supplies*

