  - *Methylprednisolone 500 mg IV over 30 minutes*
  - *Alemtuzumab 12 mg IV over 4 hours*
  - *Hourly temperature, pulse and blood pressure*
  - *First month (Day 6 – 30) – part of normal care*
  - *Valaciclovir 500 mg PO od*
  - *Bactrim DS (960 mg) PO 3 times per week (Mon, Weds, Fri)*
  - *Bloodwatch pathology tests (Every month) – part of normal care*
  - *FBC/lymphocyte subsets (4 ml) – lymphocyte subsets will be performed at weeks -1, 4, 9, 13, 26, 35, 50, 57, 61, 65, 78, 83 and 104.*
  - *EUC/LFTs (10 ml)*
  - *Urine red cell count*

[figure not shown]
- *Urine albumin*
- *UACR*
- *TSH (every 3rd month)*
- *Intervention visits (At weeks 10 and 30 provided B-cell count >30% of pre-treatment level.*
  - *Loratidine 10 mg PO 30 minutes prior to rituximab.*
  - *Methylprednisolone 100 mg IV over 30 minutes, commencing 30 minutes prior to rituximab.*
  - *Rituximab 100 mg per m^2 or placebo IV over 1 hour*
- *Monitoring visits (Every 6 months – weeks 25, 51, 77, 103, 129)*
  - *Review of relapse history*
  - *Review of adverse events*
  - *Review of intercurrent illness*
  - *Review of concomitant medications*
  - *EDSS*
  - *Monitoring visits may be conducted remotely via telehealth whether for reasons of COVID-lockdowns or remoteness of the participant*
- *MRI (Every 12 months – Baseline, Weeks 51, 103, 155)*
  - *MRI Brain*
  - *Closeout visit (Week 155 or earlier at close of study)*
  - *Review of relapse history*
  - *Review of adverse events*
  - *Review of intercurrent illness*
  - *Review of concomitant medications*
  - *EDSS*
  - *MSIS-29*
- *The timeline of participant involvement and total time commitment per patient in the trial is outlined in Table 3. Participants will also undergo the following procedures as part of normal care for someone receiving alemtuzumab. Admissions to day infusion centre for 8 hours on 5 days in year 1 and 3 days in year 2 for administration of alemtuzumab. They will also undergo monthly blood and urine tests as listed about through any private pathology firm convenient to them as part of the Bloodwatch® (RxMx®, Australia) monitoring program. The additional lymphocyte subset counts will be undertaken as part of the same blood draw and will not involve any additional tubes or time.*
- *Time constraint tolerance on study related procedures will be as follows:*
- *Screening visit, Enrolment, Review visit, EDSS and Screening bloods will be +/- 1 week.*

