**Table 3. Summary of patient participation**

Procedure	Screen	MRI Brain 1	Enrolment	Course 1	Rituximab 1	6 Month Rev	Rituximab 2	MRI Brain 2	12 Month Rev	Course 2	Rituximab 3	18 Month Rev	Rituximab 4	MRI Brain 3	24 Month Rev	30 Month Rev	MRI Brain 4	36 Month Rev	Time (Hrs)	Total Time (Hrs)
Time (wks)	-4	-1	-1	0	10	26	30	48	50	52	62	78	82	100	104	130	152	154		
Screening Visit	1																		1	1
Clinical Rev			1			1			1			1			1	1		1	0.5	3.5
EDSS	1		1			1			1			1			1	1		1	0.5	4
MRI		1						1						1			1		1	4
Screen bloods	1																		0.25	0.25
Rituximab					1		1				1		1						4	16
Total participant hours																			28.8	

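### The visit list has rituximab or placebo infused in one hour, but Tables 1 and 2 require 90 to 120 minutes for the first dose and 60 to 80 minutes for later doses

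*Protocol*

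**What the plan says.** Protocol section 3.h gives the infusion time in two places.

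- **Preparation and administration.** The instruction is "Rituximab/placebo will be administered according to Tables 1 and 2 below". Table 1 covers the first dose, in 30-minute steps at 50, 100, 150 and 200 mg/hr. Table 2 covers later doses, in steps at 100, 200 and 300 mg/hr. The text after Table 2 repeats the totals: "First infusions will typically run over 90 – 120 minutes and subsequent infusions will run over 60 – 80 minutes". It also sets a condition on stepping up: "Infusion rates should only be increased to the next phase provided there are no adverse events".
- **Study procedures and visits.** The list headed "Intervention visits (At weeks 10 and 30 provided B-cell count >30% of pre-treatment level" gives loratadine, then methylprednisolone, then rituximab 100 mg per m² "or placebo IV over 1 hour". It does not distinguish the first dose from later ones, does not mark the hour as approximate and does not refer to the tables.

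Table 3 schedules four rituximab/placebo infusions per participant and allots 4 hours to each.

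**The concern.** One section gives two durations for the same infusion, and for the first dose they do not overlap: 60 minutes against 90 to 120. Both are current text that sites act on. A visit list is what a site would naturally turn into an infusion order or checklist. The methylprednisolone line just above gives 30 minutes, which agrees with the pre-medication text, so a reader has reason to take the rituximab time literally as well.

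What is at stake is infusion safety and consistency between sites. The slow start and stepped rates give staff points at which to stop and check for a reaction before going faster. A flat one-hour infusion has no such points. It is also unclear which of the two schedules a site would be deviating from.

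**Working it through.** **Inputs, all from Protocol section 3.h.** Dose 100 mg/m²; tabulated body surface area (BSA) 1.5 to 2.5 m² in steps of 0.1, so 150 to 250 mg in 11 rows per table; the step rates of Tables 1 and 2; one hour from the visit list; 4 hours per rituximab visit from Table 3.

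**Reproducing the tables.** Each full 30-minute step delivers rate × 0.5 h, and the remainder runs at the next rate.

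- Table 1: the first three steps give 25 + 50 + 75 = 150 mg in 90 minutes. Total time = 90 + 60 × (dose − 150)/200 minutes. At 150 mg this is 90; at 250 mg it is 90 + 30 = 120.
- Table 2: the first two steps give 50 + 100 = 150 mg in 60 minutes. Total time = 60 + 60 × (dose − 150)/300 minutes. At 150 mg this is 60; at 250 mg it is 60 + 20 = 80.

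All 22 printed totals are reproduced, so the tables are sound and agree with the prose ranges.

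**Comparison with one hour.**

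| BSA (m²) | Dose (mg) | Table 1 (min) | Share given by 60 min, Table 1 | Table 2 (min) | Mean rate if given in 1 h (mg/hr) |
|---|---|---|---|---|---|
| 1.5 | 150 | 90 | 75/150 = 50% | 60 | 150 |
| 1.6 | 160 | 93 | 47% | 62 | 160 |
| 1.8 | 180 | 99 | 42% | 66 | 180 |
| 2.0 | 200 | 105 | 38% | 70 | 200 |
| 2.1 | 210 | 108 | 36% | 72 | 210 |
| 2.5 | 250 | 120 | 75/250 = 30% | 80 | 250 |

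**First dose.**

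- By 60 minutes Table 1 has delivered 25 + 50 = 75 mg, leaving 75 to 175 mg to run. No row ends at 60 minutes. A Table 1 infusion would finish in an hour only for a 75 mg dose, that is a BSA of 0.75 m², half the smallest tabulated value.
- Mean rate in Table 1: 150/1.5 = 100 mg/hr to 250/2.0 = 125 mg/hr. One hour means 150 to 250 mg/hr. The ratio is Table 1 time/60, which is 90/60 = 1.5 to 120/60 = 2.0.
- For BSA 2.1 to 2.5 (5 of 11 rows) the one-hour mean is 210 to 250 mg/hr, so the rate must at some point exceed Table 1's highest rate of 200 mg/hr.

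**Later doses.** One hour is exact at BSA 1.5 and 2 to 20 minutes short in the other 10 rows, with 10 to 100 mg still to run. The rate ratio is 60/60 = 1.0 to 80/60 = 1.33.

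**Visit time.** Methylprednisolone, infusion and 30 minutes of monitoring afterwards take 30 + 90 + 30 = 150 to 30 + 120 + 30 = 180 minutes for a Table 1 infusion, and 30 + 60 + 30 = 120 minutes for a one-hour infusion. Both fit the 240 minutes in Table 3, so the time allotted does not favour the shorter infusion.

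**The case against.** The strongest reply is that the protocol already shows which text governs. The administration section names the tables, the tables set out rate, time, dose and volume for each step, and the prose repeats the durations. The visit-list line is a brief bullet that does not claim to replace them. To go wrong, a site would have to overlook all of that. The stepping rule, premedication and half-hourly observations for at least 2 hours apply regardless, and nothing in the schedule presses a site towards an hour. For later doses the gap is at most 20 minutes. If the first dose means the participant's first, the serious conflict concerns one of four infusions. The row counts also say nothing about how many participants fall in each BSA band, and the protocol gives no reaction rate for a one-hour infusion.

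Most of this stands as mitigation. It makes harm unlikely, keeps the later-dose mismatch slight and means that no increase in reactions can be estimated. It does not reconcile the two instructions. Every participant who starts study treatment has a first infusion, and for that infusion the visit list states a time that the prescribed rates cannot achieve.

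**Conclusion.** The inconsistency is real, and the visit-list line is wrong as written. The material conflict is the first dose: the hour is 30 to 60 minutes too short, and following it would mean a mean rate 1.5 to 2.0 times that of Table 1. For later doses the shortfall is 0 to 20 minutes. These figures cover the tabulated BSA range and assume that the hour is read literally and that the tables carry the intended schedule, as the administration section indicates. Infusion safety and uniform practice across the six sites are affected. The dose in mg/m², the premedication and the primary analysis are not. It should be corrected, but it does not threaten the trial's conclusions.

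**What to change.** In section 3.h, under the intervention visits, delete the one-hour duration from the rituximab/placebo line and write: *according to Table 1 (first dose) or Table 2 (subsequent doses)*. Any site checklist or infusion order taken from the visit list should be corrected in the same way. The cost is one line of text. Dose, visit schedule, visit time and analysis stay as they are.

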## **f. Risk Mitigation Procedures**

- *Treatment with alemtuzumab is associated with a risk (6-8%) of reactivation of HSV2 infection during the first month and a much lower level risk of listeria meningitis over the same time period. As is our usual practice all participants will receive valaciclovir 500 mg once daily for 30 days and Bactrim DS 960mg three times per week for 4 weeks commencing on the first day of therapy.*
- *In view of the potential additive risk of rituximab and alemtuzumab causing an increased risk of infection all participants will be advised to report any symptoms of fever, headache, neck stiffness, photophobia, shortness of breath, cough, abdominal pain or skin lesions to site investigators immediately.*
- *In view of the known risk of autoimmune adverse events with alemtuzumab (e.g. 30% risk of autoimmune thyroid disease) all participants will be monitored with monthly blood and urine tests through the Bloodwatch program. This is PBS mandated online monitoring program for all pwMS undergoing therapy with alemtuzumab which is sponsored by the manufacturer. This is standard of care for this therapy and includes monthly urine tests for red cells and protein, monthly blood tests for full blood count, urea and electrolytes and 3-monthly blood tests for TSH levels.*
- *Regular lymphocyte subset counts will be monitored and rituximab administration will be delayed if B-cell counts do not exceed 30% of pre-treatment levels.*

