- *MRI +/- 2 weeks.*
- *Rituximab administration +/- 3 days.*

- If for clinical reasons the timing of alemtuzumab infusions must be adjusted, the timing of rituximab administration will be adjusted accordingly but the timing of all other study related procedures will remain unaltered.

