**Figure 1. RAMBLE Trial Design**

Following screening participants will be randomized 2:1 to receive either rituximab or placebo at weeks 10 and 30 after each dose of alemtuzumab. Follow up will be for a minimum of 2 years and a maximum of 4 years. Alemtuzumab administered at Week 1 and Week 53 (yellow arrows). Rituximab/placebo administered at Weeks 10 and 30 in each of Years 1 and 2 (blue arrows). Clinic reviews at -4 and -1 weeks and then every 6 months (black arrows). MRI every year (red arrows).

---

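### If alemtuzumab course 2 is rescheduled, the study dose moves but the lymphocyte subset counts appear not to, so a timely post-course count for the 30% B-cell check is no longer assured

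*Protocol*

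**What the plan says.** The Figure 1 legend has participants randomised "to receive either rituximab or placebo at weeks 10 and 30 after each dose of alemtuzumab". Table 3 puts course 2 at week 52 and the two doses that follow it at weeks 62 and 82.

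Section 3.f lists the B-cell check as a risk mitigation measure: "Regular lymphocyte subset counts will be monitored and rituximab administration will be delayed if B-cell counts do not exceed 30% of pre-treatment levels". Section 3.h repeats it as a condition of each intervention visit: "provided B-cell count >30% of pre-treatment level".

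The counts behind the check are listed in section 3.h under the Bloodwatch tests: "lymphocyte subsets will be performed at weeks -1, 4, 9, 13, 26, 35, 50, 57, 61, 65, 78, 83 and 104". The same section calls them additional to the routine draw: "The additional lymphocyte subset counts will be undertaken as part of the same blood draw and will not involve any additional tubes or time".

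The rescheduling rule closes the scheduling-tolerance bullets in section 3.h, just before Table 3. If alemtuzumab has to be moved for clinical reasons, "the timing of rituximab administration will be adjusted accordingly but the timing of all other study related procedures will remain unaltered". Those bullets allow the rituximab dose a window of plus or minus 3 days.

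**The concern.** On the planned calendar the counts serve the check well: one falls a week before the 10-week dose of year 2. The rescheduling rule, taken literally, separates the dose from that count. The protocol does not say which count releases a dose, how recent it must be, or that it must follow the latest alemtuzumab course.

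Two errors could follow if a site uses the last listed count. A count taken before the moved course says nothing about depletion from that course, and could release a B-cell-depleting dose unchecked. A count taken very soon after the course could be low and hold a dose that would qualify by its due date, pushing it outside the 3-day window. The first matters more, because section 3.f gives a possible additive infection risk of the two drugs as a reason for vigilance.

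The realistic case is course 2, since week 0 is naturally the date of course 1.

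**Working it through.** **Inputs**
- Listed count weeks (section 3.h): -1, 4, 9, 13, 26, 35, 50, 57, 61, 65, 78, 83, 104.
- Course 2 at week 52, doses at weeks 62 and 82 (Table 3).
- Delay of course 2, d weeks: not given. Assumed 0 to 44.
- Assumption on use: the site takes the latest listed count before the dose week. Nominal weeks are used throughout.
- Working cut-off: a count 5 or more weeks after the course is called usable, because the plan's own first count after course 2 is at 57 - 52 = 5 weeks. The protocol gives no B-cell levels at 1-4 weeks, so this is a convention and not a finding.

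**Formulas**
- Course at 52 + d; 10-week dose at 62 + d; 30-week dose at 82 + d.
- With L the latest listed week before the 10-week dose: weeks since course = L - (52 + d); age at dose = (62 + d) - L.

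**Planned schedule (d = 0)**
Doses fall at 62 and 82, as in Table 3. For the first, L = 61: 61 - 52 = 9 weeks after the course and 62 - 61 = 1 week old. For the second, the latest count is week 78: 26 weeks after the course and 4 weeks old.

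**10-week dose after a delay**

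| Delay d (weeks) | Latest listed count | Weeks after course | Age at dose (weeks) |
|---|---|---|---|
| 1-3 | 61 | 8 to 6 | 2 to 4 |
| 4-8 | 65 | 9 to 5 | 1 to 5 |
| 9-12 | 65 | 4 to 1 | 6 to 9 |
| 13 | 65 | 0 (course week) | 10 |
| 14-16 | 65 | 1 to 3 before | 11 to 13 |
| 17-21 | 78 | 9 to 5 | 1 to 5 |
| 22-26 | 83 | 9 to 5 | 1 to 5 |
| 27-30 | 83 | 4 to 1 | 6 to 9 |
| 31 | 83 | 0 (course week) | 10 |
| 32-42 | 83 | 1 to 11 before | 11 to 21 |
| 43-44 | 104 | 9 to 8 | 1 to 2 |

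Example, d = 14: course at week 66, dose at week 76, latest count week 65. That is 1 week before the course and 76 - 65 = 11 weeks old. At d = 16 and d = 42 a listed count (week 78, week 104) falls in the dose week and may rescue the check.

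**30-week dose after a delay**
A post-course count precedes it at every delay from 0 to 44 weeks. At d = 21 the doses fall at weeks 83 and 103, and the latest count (week 83) is in the week of the first. At d = 22 they fall at weeks 84 and 104. The latest count (week 83) is then a week before the first dose, and another falls in the week of the second. At d = 42-44 the last listed count (week 104) is in the week of the moved 10-week dose or before it. In these cases no listed count falls clearly between the two doses.

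**After the fix**
Weeks 57, 61, 65, 78 and 83 are 5, 9, 13, 26 and 31 weeks after week 52. Dated from the actual course, the 9-week count is always 1 week before the 10-week dose. The 26-week count is always 4 weeks before the 30-week dose and 16 weeks after the 10-week one.

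**The case against.** The reading is open to dispute. The tolerance bullets name visits, EDSS, screening bloods, MRI and rituximab, but not the later subset counts. Those counts are also absent from Table 3 and sit under a heading that marks the Bloodwatch tests as routine care. A site could conclude that the rule does not hold them fixed. Against this, section 3.f does not include subsets in the Bloodwatch panel, and section 3.h calls them additional. The text is ambiguous, which itself calls for a clarifying sentence.

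The check also implies a meaningful count. Section 3.b describes sites led by MS subspecialists with experience of both drugs, who may not accept a pre-course count as evidence of recovery. Nothing forbids an unscheduled count, and where the last count is 6-9 weeks old a monthly draw falls in between. This stands, and it limits the likely harm. But no text requires that count, and the monthly full blood count does not measure B-cells.

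A reader might infer that after any delay the plan requires no post-course count. It does not go that far: the listed weeks supply one before the 10-week dose at delays of 1-12 and 17-30 weeks, and always before the 30-week dose. A reader might also note that 12 of the delay values from 1 to 30 (9-16 and 27-30) are unsatisfactory and treat that as a rate. It only counts grid values, and it mixes early counts, which mainly risk a needless hold, with missing ones.

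**Conclusion.** The point holds in a limited form. On the natural but not certain reading, the planned count one week before the 10-week dose is no longer assured once course 2 moves. The clear gap is at delays of about 13-16 weeks, and 31-42 weeks if delays run that long: the 30% check could then rest on a count that does not reflect the latest course. Delays of 9-12 and 27-30 weeks leave only an early, ageing count. Delays of 1-8 and 17-26 weeks leave a usable one. The 30-week dose is affected only in that, at delays of 21-22 weeks (and 42-44), no count falls clearly between the two doses.

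This rests on the assumed range of delays and on a site using the last listed count. The protocol gives no frequency of delays, so the number of participants affected is unknown. A reader might infer a bias in the primary comparison; nothing in the protocol shows one. Minor; a cheap improvement to a listed safety measure.

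**What to change.** Amend the rescheduling sentence in section 3.h so that the post-course-2 subset counts (now weeks 57, 61, 65, 78 and 83) are taken 5, 9, 13, 26 and 31 weeks after the actual date of course 2. Add a second sentence: each dose is released on a count taken after the alemtuzumab course it follows and, for the 30-week dose, after the preceding study dose; normally these are the 9-week and 26-week counts. The other listed counts, MRI, EDSS and clinic reviews can stay on calendar weeks.

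The number of counts stays at 13, and by the protocol's own account they share the monthly draw without extra tubes. The cost is that test request dates must be set per participant, and the monthly draw day may need realigning to the moved course.
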